Study data will be collected using self-report surveys at baseline, 6, 10- and 14-months; biochemical measures of percent time with hypoglycemia and number of biochemical hypoglycemic events using CGM at baseline and 14 months; and data extracted from the EHR for Hemoglobin A1c and hypoglycemia-related healthcare utilization at baseline and 14 months. The outcomes are described in section 2d, above.

4a.1 Self-report measures:

All self-report instruments are included in **Appendix C**. Survey questions will be administered at baseline and all follow up time points (6, 10 and 14 months) by telephone by trained KPHRI survey research program (SRP) staff. Telephone data collection will be performed using Sawtooth Ci3 and WinCATI computer-assisted telephone interviewing (CATI) software. SRP Interviewers are trained in standardized survey interviewing techniques, use of the CATI system, and will be trained in project-specific procedures including item-by-item specifications for each questionnaire. Interviewers' phone performance, productivity, and response rates are routinely monitored; corrective or remedial training is provided if necessary. Interview quality is continuously assessed using silent monitors installed on all telephones; completed interviews are edited and coded within 48 hours, and interviewer feedback occurs on a regular basis. SRP Interviewers are certified in NIH Human Subjects Protections.

4a.2. CGM data:

CGM data will be collected at baseline and 14 months using the Dexcom 6G Pro CGM integrated sensors and transmitters in blinded mode. We chose Dexcom sensors because of validity, reliability, ability to record glucose measurements blinded to the participant; and the ability to store up to 10 days of data. At both timepoints we will collect 10 days of CGM readings. The readings will be blinded at the time of data collection but shared with the participant at the end of the study.

Baseline CGM data will be collected after collection of baseline self-report data but before beginning any intervention activities. CGM data at 14-months will be collected at the same time as outreach for 14-month follow up self-report. In both cases the process will be the same:

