The study nurse or medical assistant (MA) will telephone the participant and schedule a CGM virtual visit. S/he will then mail the sensor-transmitter unit (programmed to keep glucose readings blinded from the participant) and instructions to the participant, along with postage-paid packaging to return at the end of the 10-day recording period. At the virtual visit, the nurse or MA will walk the participant through placing the device, will answer any questions and will provide a telephone number that the participant can call for questions or issues that may come up. The participant will then wear the device for 10 days with readings stored on the unit. The study nurse or MA will make one follow up call near the end of the 10 days, to check in, answer questions and confirm that the participant will remove and mail back the single use sensor-transmitter on the planned date. At the end of the recording period the participant will remove and mail back the device using the provided mailing materials. The data will then be read or downloaded from the sensor-transmitter using the DexCom 6G Pro reader/receiver.

4a.3 EHR data:

The study programmer will extract data from the EHR to assess study eligibility for recruitment and collect outcome measures including HbA1c and hypoglycemia related health care utilization, including emergency department and urgent care visits and hospitalizations. If participants are asked to have an HbA1c at 14 months, the results will be collected from the medical record in the same way as other HbA1cs.

4a.4 Data collection incentives:

Participants will be mailed \$100 for completion of baseline and 14-month follow up study measures (\$30 for the survey and \$70 for CGM at each time point). They will be mailed \$30 for completion of self-report-only measures at 6- and 10-month follow up. Participants who agree to have an HbA1c test for the study at months will be mailed an additional \$25.

4a.5 Procedures for participants not completing study activities, or withdrawing consent

[figure not shown]

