The DSMB will receive ongoing reports to ensure data validity and integrity, including recruitment reports, participant characteristics by study arm to ensure adequacy of randomization and balanced enrollment, participant completion of study visits, and completeness of study data collection. The DSMB may also choose to see outcome data, with this data blinded except to the study biostatisticians. If the DSMB deems it necessary to unblind themselves to interim trial reporting this may occur, similarly the DSMB may decide to unblind the study Principal Investigator if patient safety is a concern.

We do not propose interim analyses or stopping guidelines. The assessment of the primary outcome requires 14 months of follow-up from baseline; the study enrollment period is only 8 months long, therefore enrollment (and likely study interventions) will be complete for all participants before primary outcome data is available on

any participants. We cannot feasibly stop the trial for futility or harms seen on the primary outcome before the end of enrollment.

4d.2 Harms

Adverse events: For this study an adverse event will be defined using the definition from 21 CFR 312.32 (a) as any *untoward medical occurrence in a participant without regard to the possibility of a causal relationship*. Adverse events will be collected after the participant has provided consent and enrolled in the study and through 14-month follow up.

Adverse events will be collected using self-report open-ended survey questions at all follow up data collection timepoints, including 6-month, 10-month and 14-month follow ups. Adverse events will be classified as to whether they are:

1. Expected or unexpected in nature, severity, or frequency for the population under study (i.e. not mentioned in study documents or consent);
2. Related or possibly related to the study procedures or participation in the research; and
3. Serious adverse events (SAE) or not.

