In addition, adverse events will be reported on an expedited basis that are: (1) unexpected; and (2) related or possibly related to study procedures or participation in the research; and (3) suggests that the research places subjects or others at a greater risk of harm than was previously known or resulted in a serious adverse event (SAE). Per institutional reporting requirements these events will be reported within 1 business day of discovery if a death or within 15 days for other serious adverse events.

If a participant experiences an adverse event after informed consent is completed but before the participant has started to receive the study intervention, the event will be reported as not related to the study intervention.

5. Ethics and dissemination

5a. Research ethics approval

This protocol and all informed consent scripting and documentation (sample text included in **Appendix A**) will be reviewed and approved by the KPWRHI IRB with respect to compliance with applicable research and human subjects regulations. The KPWHRI IRB will also review participant recruitment, intervention and data collection materials and plans, any other requested documents and any subsequent modifications. No activities involving human subjects will take place unless they have been reviewed and approved. Subsequent to initial review and approval, the KPWHRI IRB will review a continuation and progress report at least annually. These reports will include the total number of participants enrolled, a report on study progress, summaries of adverse events and summaries DSMB meetings and recommendations.

5b. Protocol amendments

Any modifications to the protocol which may impact on the conduct of the study, potential benefit for the participant or may affect participant safety, including changes of study objectives, study design, participant population, sample sizes, study procedures, or significant administrative aspects will require a formal amendment to the protocol. Such amendments will be agreed upon by the study investigators and will be submitted for review and approval by the KPWHRI IRB prior to implementation.

Administrative changes of the protocol are minor corrections and/or clarifications that have no effect on the way the study is to be conducted. These administrative changes will be agreed upon by the study investigators and will be

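### Adverse-event collection is not tied to either CGM wear, and one relatedness scale serves both the intervention and data collection

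*Combined protocol and SAP*

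**What the plan says.** Section 4d.2 (Harms) sets the period: "Adverse events will be collected after the participant has provided consent and enrolled in the study and through 14-month follow up". It then gives the method: "Adverse events will be collected using self-report open-ended survey questions at all follow up data collection timepoints, including 6-month, 10-month and 14-month follow ups". No other scheduled method is described.

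The same section lists sensor complications among the expected adverse events: infection, bleeding, pain, skin irritation and, remotely, a retained wire. Participants with such problems are directed to the Endocrinology service.

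Section 4a.2 (CGM data) describes the two wears. On the first: "Baseline CGM data will be collected after collection of baseline self-report data but before beginning any intervention activities". On the second: "CGM data at 14-months will be collected at the same time as outreach for 14-month follow up self-report". Each wear begins with a scheduling call; "S/he will then mail the sensor-transmitter unit", a virtual visit follows for placement, and the device is worn for 10 days. Participants receive a telephone number for problems, and "The study nurse or MA will make one follow up call near the end of the 10 days". That call is for checking in, answering questions and confirming removal and return.

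On relatedness, 4d.2 has an independent physician rate each event on one five-level scale that covers the intervention or data collection. An event after consent is treated separately if it occurs early: "but before the participant has started to receive the study intervention, the event will be reported as not related to the study intervention".

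**The concern.** Apart from an HbA1c blood draw in some participants, placing and wearing the sensor is the study procedure for which the protocol itself describes physical risks. It is done twice, yet the adverse-event questions follow the survey calendar. Minor skin reactions are easily forgotten over several months, and a survey completed before a wear cannot record what happens during it. Under-capture of this kind can only lower the complication rate seen by the DSMB and the IRB, who receive the adverse-event reports.

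The relatedness text adds a coding problem. The rule for events before the intervention speaks of the intervention alone, but the scale on which it would be recorded speaks of study procedures in general.

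**Working it through.** The documents give no sensor complication rate, so the number of events missed cannot be calculated. The check is of timelines and definitions.

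**First wear**
- Start: after the baseline survey and before any intervention activity (4a.2).
- Assumed timing: months 0 to 2, because 2d.1 allows two months for baseline CGM and intervention activities before the 12-month outcome window.
- First adverse-event question: month 6 (4d.2).
- Recall interval: 6 − 2 = 4 months to 6 − 0 = 6 months.
- The wear lies inside the stated collection period, provided it follows written consent. The text implies this without stating it. The weakness is the length of recall.

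**Second wear**
- The wear is tied to outreach for the 14-month survey, and 4a.2 fixes no order between survey and wear.
- If the survey is answered at the outreach contact, scheduling, mailing and placement still lie ahead, so all 10 wear days follow the last question.
- If the survey is answered after the device is returned, none do.
- Range per participant: 0 to 10 wear days uncovered.
- Number of wears: 2f plans 128 per arm with 80% response. 128 × 0.80 = 102.4, which the protocol takes as 102 per arm, so 2 × 102 = 204. Applying this survey response rate to the sensor is an assumption.
- Range for the trial: 0 to about 204 second wears could end after the last question.

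**Other contacts**
- The end-of-wear call happens before the device is removed, and no adverse-event question is specified for it. A problem at removal would fall after the call in any case.
- Neither the help-line number (4a.2) nor the referral to Endocrinology (4d.2) is said to lead to a study adverse-event record.

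**Relatedness, set side by side (all in 4d.2)**
- Classification asks about relation to study procedures or participation.
- The physician's scale asks about relation to the intervention or data collection.
- The lowest category on that scale describes an event wholly independent of study procedures, and/or one with evidence that another cause is definite.
- The rule for early events makes them unrelated to the intervention.

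Take a skin infection at the sensor site during the first wear. It meets the condition of the early-event rule, yet it does not fit the lowest category if the sensor caused it. With one rating field, a coder who follows the rule could enter the lowest category for an event caused by a study procedure.

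**The case against.** Several stronger readings are tempting, and the documents do not support them.

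- **That the second wear always follows the last question.** The text ties the wear to survey outreach and fixes no sequence. CGM is one of the 14-month measures, so the stated end of collection can be read to include the wear. This stands as an objection to any claim that second-wear events are certainly lost. It does not supply a question after the wear.
- **That the collection period misses the first wear.** It does not. The event can be reported at month 6.
- **That every first-wear event is declared unrelated to the study.** The early-event rule is limited to the intervention, and relation to procedures is kept elsewhere in 4d.2. What remains is the risk of miscoding on a shared scale.
- **That an event at the final wear cannot reach expedited reporting.** The reporting clock runs from discovery, by whatever route. Section 4d.1 also has the team track participant-reported serious adverse events without confining this to surveys. The complications listed as expected would not meet the unexpectedness criterion in any case.
- **That the counts of wears measure what is missed.** Of 256 + 204 = 460 planned wears, 204 are second wears (44%) and 256 are first wears (56%). These are shares of wears, not of lost events. The first figure is a ceiling that depends on survey order, and the second counts wears to which the early-event rule applies, without implying miscoding.

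It is also fair to say that both arms undergo the same blinded CGM procedure, that the protocol describes insertion complications as uncommon, and that the primary outcome is untouched. Recruitment is listed as complete and the latest version is dated 04/14/2025, so some or all wears may be over. The documents do not say. These points limit the importance of the finding but do not remove it.

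**Conclusion.** The concern holds as a gap in safety capture that is cheap to close. No scheduled adverse-event question is tied to either wear, although sensor complications are named as expected events. First-wear complications rest on about 4 to 6 months' recall, assuming a wear in months 0 to 2. Between 0 and about 204 second wears could end after the last question, assuming that all of the 80% of responders wear the sensor. The actual number depends on the order of survey and wear, which the protocol leaves open. Contacts about sensor problems have no stated path into the adverse-event record, and the single relatedness scale allows a first-wear event to be miscoded. Any bias in the reported complication rate is downward, but the documents give no figure from which to size it. The primary efficacy analysis is not affected.

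**What to change.** In 4d.2:

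1. Add an adverse-event question to the end-of-wear call that 4a.2 already provides at both wears, and a check when the device is returned, so that problems at removal are also covered.
2. State that collection runs until the 14-month sensor has been returned.
3. Record relation to the intervention and relation to data-collection procedures as two separate ratings, and apply the early-event rule to the first only.
4. State how sensor-related contacts with the help line or Endocrinology enter the adverse-event record.

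For wears already finished, compare 14-month survey dates with wear dates to find how many wears ended after the last question, retrieve sensor-related Endocrinology contacts from the EHR, and disclose the limitation when safety results are reported.

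The cost is a few sentences in 4d.2, one question in an existing call, a brief check at device return and a second rating field. The downside is a few more minor skin events to log.

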We estimate 256 patients (128 randomized to proactive care management, and 128 randomized to MyHC-T2D) will consent and complete the baseline survey. To account for loss to follow-up, we assume an 80% response rate for the primary outcome measured at 14-months, for an analytic sample size of 204 (102 per group). Power calculations for comparing two independent proportions and assumed a 0.05 type I error rate. Assuming 60% of patients in the proactive care management group will self-report having had a severe hypoglycemia event in 12-month look back (yes/no), we have 90% power to detect a 22.6% absolute difference between groups (i.e. 37.4% severe hypoglycemia rate in MyHC-T2D arm) for the primary outcome. We have 80% power to detect an absolute difference of 19.7% between groups. Our study has power to detect a meaningful difference (30% or more reduction in frequency of self-reported severe hypoglycemia events).⁵⁴ Other studies including for the original *my hypo compass* have similar or larger effects on severe hypoglycemia reductions.²⁵⁻²⁹ We also have 80% power to detect a 1.4% difference and 90% power to detect a 1.6% difference between groups in the secondary outcome of the percent time with biochemical hypoglycemia (<54 mg/dL); this difference is consistent with the effect seen with the original *my hypo compass*.^{25,32}

2g. Recruitment

We will recruit the study population in two steps.

Step 1, Automated risk stratification: We will identify a cohort of adults (≥ 18 years) with T2D receiving primary care at KPWA. We will identify all individuals with either a current prescription for insulin or who have intermediate-to-high risk for a SH event based on our hypoglycemia risk-stratification tool.

Step 2, Phone screening for verbal consent and to identify patients at highest SH risk: We will mail eligible participants an invitation with study brochure and notification that staff will call them about the study. KPHRI Survey Research Program (SRP) members will then call the potential participant to explain the study, assess eligibility and interest, and conduct informed verbal consent with those who are eligible and interested. We expect 1001 eligible. Based on a similar recruitment⁵⁵ and participation in other diabetes education trials, we anticipate at least 25% will consent and complete baseline data collection.⁵⁶

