Process Evaluation: We will use descriptive analysis to assess intervention recruitment, reach and delivery. If significant differences ($p<0.05$) between intervention groups are found for the primary outcome, we will perform mediation analysis to test the hypothesis that the possible causal pathway for reducing the occurrence of severe hypoglycemia is through improvements in hypoglycemia knowledge, hypoglycemia awareness, self-efficacy of hypoglycemia management, blood glucose testing, and hypoglycemic medication adjustment and other factors in causal pathway in **Figure 2**. Mediation analysis will use a regression-based approach within the causal mediation framework,⁵³ separating the total intervention effect into a natural indirect effect (effect occurring through the mediator), and a natural direct effect (effect through all other pathways). To estimate these effects, we will use either a log-linear or Poisson model for the outcome model (depending on whether the primary outcome is defined as a binary or count variable), and linear regression for the mediator model. The effect of each mediator will be estimated in separate models.

4d. Trial monitoring

4d.1 Data monitoring

This study will have a Data Safety Monitoring Board (DSMB) to ensure safety of research participants. The DSMB will include an external researcher with prior DSMB experience (the chair), and two clinicians with expertise in type 2 diabetes and in the treatment and care for patients with severe hypoglycemia and impaired hypoglycemia awareness. The DSMB will meet once in the first 6 months after study funding and prior to patient enrollment to review study protocols and plans for study reports (enrollment, completion, and adverse event-reporting tables by study group) and recommend changes. The study team will track participant-reported serious adverse events whether related or not to study participation. The team will provide ongoing reports to the DSMB and the Institutional Review Board. The DSMB will meet twice per year, in person or by phone, as directed by the committee. The study Principal Investigator, biostatisticians, and project manager will attend all open portions of DSMB meetings.

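### AEs and SAEs are ascertained only by participant self-report at 6, 10 and 14 months, so deaths, and non-hypoglycemia admissions after the last completed survey, have no stated detection route

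*Combined protocol and SAP*

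**What the plan says.** Section 4d.2 (Harms) sets the collection window: "Adverse events will be collected after the participant has provided consent and enrolled in the study and through 14-month follow up". It then gives the method: "Adverse events will be collected using self-report open-ended survey questions at all follow up data collection timepoints", listed as 6, 10 and 14 months. Section 4d.1 (Data monitoring) agrees: "The study team will track participant-reported serious adverse events whether related or not to study participation". Neither section names a chart review, death check, proxy report or route from nurse to study team.

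The SAE definition in 4d.2 includes death and inpatient hospitalization for any cause. AEs go to the DSMB at every meeting and to the IRB at least yearly. Events that meet the expedited criteria are due within 1 business day (deaths) or 15 days (other SAEs), counted from discovery.

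The EHR has a different use. Under 4a.3 the programmer will "collect outcome measures including HbA1c and hypoglycemia related health care utilization, including emergency department and urgent care visits and hospitalizations". Section 2d.2 limits that utilization outcome to visits with hypoglycemia as the primary or principal diagnosis, and 4a says it is collected at baseline and 14 months. Section 4a.5 keeps EHR extraction going for people who skip activities without withdrawing consent.

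**The concern.** The definition of an SAE and the means of finding one do not match. Two of the listed SAE criteria, death and hospitalization, are the events most likely to stop someone answering a telephone survey. The gaps in the SAE tables would then depend on the events themselves.

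Three features of this trial add weight:

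- Section 4d.1 plans no interim analyses or stopping guidelines, so the AE tables by study group are a main safety input to the DSMB.
- The MyHC-T2D program runs for about three months (section 2e), and the first AE question comes at month 6. An event can go unknown for up to six months even in someone who answers every survey. The reporting clock starts only at discovery.
- Chance discovery by nurses may not be even across arms. The MyHC-T2D arm has two group sessions, a review call and a booster call beyond the outreach that both arms receive (section 2c.2).

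For efficacy, section 4c sets an attrition level (10%) above which selection bias is to be addressed. Nothing comparable exists for safety.

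**Working it through.** **Step 1. Reproduce the plan's follow-up figure.** Inputs from section 2f: "We estimate 256 patients (128 randomized to proactive care management, and 128 randomized to MyHC-T2D) will consent and complete the baseline survey", and "we assume an 80% response rate for the primary outcome measured at 14-months".

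- 256 × 0.80 = 204.8, which the plan takes as 102 per arm, or 204. The figure reproduces.
- 256 − 204 = 52 participants expected without month-14 primary outcome data (52 / 256 = 20.3%).

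**Step 2. Match each kind of SAE to its stated route.**

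| Event | Self-report survey | EHR as planned | Stated route into the AE record |
|---|---|---|---|
| Death | Not possible | Not named | None |
| Non-hypoglycemia admission before the last completed survey | Yes, if recalled | Not extracted | Survey |
| Non-hypoglycemia admission after the last completed survey | No | Not extracted | None |
| Hypoglycemia admission (primary or principal diagnosis) after the last completed survey | No | Yes, as an outcome, if not withdrawn | None stated |

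The death row does not depend on the response rate. Anyone who dies before the 14-month survey becomes a non-responder, and the death falls after their last survey.

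**Step 3. Can the number of missed SAEs be given?** It would be about 52 × r × f. Here r is the 14-month risk of an SAE in these participants, and f is the share of follow-up after their last completed survey. The documents give neither.

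- Never answered: f = 14/14.
- Last answered at month 6: f = (14 − 6)/14 = 8/14.
- Last answered at month 10: f = (14 − 10)/14 = 4/14.

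To show how wide the answer is, assume r between 10% and 40%, with events spread evenly over time:

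- f = 14/14: 52 × 0.10 = 5.2, to 52 × 0.40 = 20.8.
- f = 8/14: 3.0 to 11.9.
- f = 4/14: 1.5 to 5.9.

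These ranges include hypoglycemia admissions, which the EHR outcome would show. They illustrate how far the answer depends on unknown inputs and are not estimates.

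**The case against.** The plan is less exposed than a quick reading suggests, and four stronger readings should be set aside.

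- **All SAEs in a fifth of participants are lost.** A reader might infer this from the 80% response rate. That rate is for the primary outcome at month 14. AE questions are also asked at 6 and 10 months, with repeated calls, so some of the 52 will have reported earlier events.
- **All admissions in non-responders are lost.** Hypoglycemia admissions, the ones closest to the trial's purpose, are extracted from the EHR, and 4a.5 continues that extraction unless consent is withdrawn. What is missing is a link from that outcome to AE classification.
- **The study already holds all-cause admissions.** It does not. The planned extraction is restricted to hypoglycemia, so the remedy needs a wider query.
- **Harms from the 14-month CGM wear always fall after the last AE question.** Section 4a.2 says only "CGM data at 14-months will be collected at the same time as outreach for 14-month follow up self-report" and does not fix the order of interview and wear. Participants also have a help number, a call near day 10 and a clinical service to contact. None of these is labelled AE collection, so a gap is possible but not certain.

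It can also be said that the intervention is education added to care both arms receive, that the protocol expects no added risk, and that the DSMB sees completeness reports and can ask for changes. Finally, recruitment is complete, so new prospective procedures may come too late for most participants.

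All of this limits the size of the problem. None of it supplies a way to learn of a death, or of a non-hypoglycemia admission after the last survey. Completeness reports would show the DSMB that data are missing, but not what happened to those participants.

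**Conclusion.** The point holds in a limited form. As written, 4d.1 and 4d.2 rely on participant self-report alone. Deaths at any time, and non-hypoglycemia admissions after the last completed survey, have no stated detection route. Hypoglycemia admissions are detected but not routed to AE classification. The by-arm SAE tables would therefore probably be incomplete in a way related to the events, whether or not response differs by arm.

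Up to 52 of 256 participants are expected to lack month-14 data, and the exposure is largely among them. The number of missed SAEs cannot be stated: the documents give no SAE rate and no pattern of response at 6 and 10 months. Informal discovery, for example when a survey call reaches a relative, is not excluded, but no procedure is set out for it.

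The sample size, power and primary comparison are unaffected. This is a change that should be made for the safety report, not a flaw in the efficacy design.

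**What to change.** In section 4d.2:

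1. Add extraction of deaths and all-cause hospitalizations from EHR and administrative data for every randomized participant who has not withdrawn. First confirm that the signed consent covers it.
2. Run it before any remaining DSMB report and once as a look-back through month 14. The look-back works although recruitment is complete.
3. Tabulate these events by arm beside the self-reported ones, and send both, including hypoglycemia admissions already held as an outcome, to the same AE classification.
4. Where 14-month CGM wears remain, optionally record AEs on the call already made near day 10 (section 4a.2).

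**Cost.** Section 4b describes a warehouse covering enrollment, diagnoses and procedures, so the work is mainly a wider query. That section does not list deaths, so their source must be confirmed. The main downside is more unrelated events for the independent physician reviewer. There is also a limit on coverage: eligibility asks only for an intention to stay in the health plan for 6 months, so records may stop before month 14 for some people. The report should give each arm's length of EHR coverage.
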